6.4 STUDY INTERVENTION COMPLIANCE

Investigational site compliance with all study procedures, including randomization assignment and treatment, will be monitored by trained and qualified study sponsor representatives and/or designees.

7 VFSS STOPPING CRITERIA AND PATIENT/SITE/STUDY TERMINATION

7.1 VFSS STOPPING CRITERIA

• If the PAS is ≥ 6 (see below) for three consecutive bolus trials of the same consistency, that consistency should be stopped and the investigator (or trained and authorized designee) can decide if it is safe to move to the next consistency to assess dietary modification, or if the study needs to be stopped.

Penetration Aspiration Score Definitions:

- Score = 6: Material enters the airway, passes below the vocal folds and is ejected into the larynx or out of the airway.
- Score = 7: Material enters the airway, passes below the vocal folds & is not ejected from the trachea despite effort
- Score = 8: Material enters the airway, passes below the vocal folds & no effort is made to eject
- A 'Stop' may be applied at any time if the Investigator (or trained and authorized designee) feels it is unsafe for the patient to continue.
- If VFSS time exceeds 3 minutes, the procedure must be stopped.

Regardless of completion of the PES treatment, patients will be encouraged to remain in the study until they have completed the protocol-required follow-up period while maintaining respect for all patient rights. Patients are free to withdraw from participation in the study at any time upon request.

7.2 PATIENT TERMINATION

Possible reasons for premature patient termination include but are not limited to the following:

• Withdrawal of consent: The patient decides to withdraw from the study. If a patient withdraws from the clinical investigation, the reason(s), if known, will be

CONFIDENTIAL Page 43 of 71

recorded on the eCRF. If withdrawal is due to problems related to the investigational device safety or performance, the investigator shall ask the patient's permission to follow his/her status/condition outside the investigation.

Lost to follow-up: If a patient has been discharged to inpatient care at another institution, then attempts should be made to retrieve patient records from that institution. Telephone follow-up at 11 weeks (+/- 1 week) should be attempted at least three times. If the patient does not respond to the three telephone calls, then the investigator should send a letter to the patient. All attempts should be documented in the source documents and on the eCRF. A patient will be considered lost to follow up if more than 30 days has elapsed from last contact. Patients who discontinue prematurely will be included in the analysis of results and will not be replaced.

An investigator may discontinue or withdraw a patient from the study for any reason, including the following:

- Pregnancy
- Significant non-compliance with study protocol
- If any clinical adverse event (AE), laboratory abnormality, or other medical condition or situation occurs such that continued participation in the study would not be in the best interest of the patient
- Disease progression which requires discontinuation of the study intervention
- If the patient meets an exclusion criterion (either newly developed or not previously recognized) that precludes further study participation

The reason for termination from the study will be recorded on the eCRF. Patients who sign the informed consent form and are randomized but do not receive the assigned study intervention (whether sham or treatment) may be replaced to achieve the number of evaluable patients needed for analysis. Patients who receive treatment but discontinue the study prematurely for any reason will not be replaced.

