STUDY OBJECTIVES	STUDY ENDPOINTS			
To evaluate the efficacy of	General stroke health outcomes will be			
Phagenyx® treatment on general	assessed by:			
stroke health outcomes.	 Time to discharge from site in which treatment is received Discharge destination from the site in which treatment is received Patient location (home, institution) at 11 weeks Days on antibiotics during hospital stay NIH Stroke Scale (NIHSS) at baseline and 14 days or discharge, and 11-week follow up Modified Rankin Scale (mRS) at baseline, 14 days, and 11 week follow up Barthel Index (BI) at baseline, 14 days or discharge, and 11-week follow up New onset pneumonia, using a standardized definition adapted from the STROKE-INF study²⁶ at baseline, 48 hrs, 7 days, and 14 days or discharge Hospital readmission rate Number of CXR (related to suspect pneumonia) 			

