5.2 EXCLUSION CRITERIA

An individual who meets any of the following criteria will be excluded from participation in this study:

- 1. Brainstem stroke.
- 2. Evidence of traumatic brain injury or subarachnoid hemorrhage.
- 3. Other, non-cerebrovascular, structural brain diseases, including multiple sclerosis or other demyelinating diseases, brain tumors (other than small meningioma), neurodegenerative diseases (including Alzheimer and Parkinson disease), hydrocephalus, and leukodystrophy
- 4. Dysphagia from conditions other than stroke.
- 5. Pre-stroke history of swallowing complaints or treatment or history of diseases known to be associated with swallowing problems (other neurological, head and neck cancer.
- 6. Distorted oropharyngeal anatomy (e.g., pharyngeal pouch, major pharyngeal surgery or head /neck surgery)
- 7. Currently being treatment for pneumonia.
- 8. Mute, global aphasia; no usable speech or auditory comprehension (scores 3 on NIHSS question 9, Best Language)
- 9. NIHSS score of 25
- 10. Presence of a tracheostomy
- 11. Any active implanted device (e.g., cochlear implant, ICD, permanent pacemaker)

CONFIDENTIAL Page 35 of 71

- 12. Any progressive neurological disorder (e.g., Parkinson's Disease, Multiple Sclerosis)
- 13. Cognitive impairment that prevents compliance with protocol-specific instructions and assessments
- 14. Unstable cardiopulmonary condition, i.e., not on maintenance therapy.
- 15. Currently participating in another investigational study
- 16. Pregnant or planning to become pregnant while participating in the clinical study
- 17. Known Allergy to oral radiographic contrast media (specifically barium)
- 18. Any other condition in the opinion of the investigator will prohibit the patient from participation and follow up.

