9.4.2 ANALYSIS OF THE PRIMARY EFFICACY ENDPOINT

The primary analysis will be performed on the ITT population. The primary endpoint is trichotomized PAS on each bolus, determined by VFSS 48 hours after completion of PES treatment. The three ordinal PAS categories are defined as Safe (PAS 1-3),

CONFIDENTIAL Page 56 of 71

Penetration (PAS 4-5), and Aspiration (PAS 6-8). Each patient contributes 12 measurements to the primary endpoint, of which 6 are from boli of a thin consistency and 6 are from boli of a nectar consistency.

Missing PAS data will be imputed in the primary analysis. PAS values that are missing due to application of VFSS stopping criteria will be assigned the worst (highest) post-treatment PAS value. For patients who have no post-treatment PAS data due to lost-to-follow-up or death, the post-treatment PAS values will be imputed from baseline PAS values and other patient baseline characteristics using multiple imputation. In addition, tipping point analysis will be performed as a sensitivity analysis.

A cumulative logistic model will be used to analyze the primary endpoint, and a sandwich variance estimator via a generalized estimating equations approach will be used to account for correlated PAS outcomes within each patient. Modeling details are specified in the SAP.

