4.6.2 Secondary Efficacy Analysis

The secondary endpoints are FIOS and DSRS 7 days (+/- 1 day) after completion of investigational treatment.

The ordered categorical endpoint of FIOS will be analyzed by a Cochran-Mantel-Haenszel (CMH) test stratified by site and baseline PAS, using the modified ridit score and test of "row mean scores different" to take into account the ordered nature of the response.

The secondary endpoint of DSRS will be modeled by an ANCOVA model with treatment, center, baseline PAS and baseline DSRS as predictors, and will be tested for statistical significance provided the primary endpoint is found to be statistically significant. The ITT population will be used.

Missing data on the secondary endpoint will not be imputed for the purpose of significance testing.

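### Protocol 7.2 lets a randomised patient be withdrawn from the study for newly meeting an exclusion such as pneumonia treatment, so loss of the 48-hour PAS and 7-day FOIS/DSRS can depend on outcome

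*Protocol*

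**What the plan says.** Protocol 7.2 introduces its list with "An investigator may discontinue or withdraw a patient from the study for any reason, including the following". One item is "If the patient meets an exclusion criterion (either newly developed or not previously recognized) that precludes further study participation"; another covers adverse events and other medical conditions that make continued participation unwise. The withdrawal is from the study, not only from treatment. Neither document says which newly developed exclusions preclude participation, and neither exempts pneumonia.

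Exclusion 7 in Protocol 5.2 is "Currently being treatment for pneumonia". Two exploratory endpoints in Protocol 3 concern the same illness: "New onset pneumonia, using a standardized definition adapted from the STROKE-INF study" and "Days on antibiotics during hospital stay".

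Protocol 7.1 favours retention: "Regardless of completion of the PES treatment, patients will be encouraged to remain in the study until they have completed the protocol-required follow-up period". Protocol 7.2 also keeps patients who discontinue early in the analysis, and Protocol 9.3 defines ITT as everyone randomised.

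For the primary endpoint, Protocol 9.4.2 and SAP 4.6.1 (printed under SAP 4.8) say in general terms that missing PAS is imputed. They then give a method for stopped examinations and, by multiple imputation from baseline data, one introduced with "For patients who have no post-treatment PAS data due to lost-to-follow-up or death". A tipping-point analysis is added. For the secondaries, SAP 4.6.2 says "Missing data on the secondary endpoint will not be imputed for the purpose of significance testing".

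**The concern.** Entry criteria normally stop operating at randomisation. Here they can be applied afterwards, and one of them describes an illness that aspiration tends to cause. Aspiration (PAS 6–8) is the worst category of the primary endpoint. Protocol 2.1 cites a pooled relative risk of pneumonia of 11.56 (95% CI 3.36–39.77) with confirmed aspiration. The patients most open to removal are therefore likely to be among those who would have scored worst.

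If a site uses the provision, whether the 48-hour PAS and the 7-day FOIS and DSRS are observed can depend on how the patient is doing. If pneumonia rates differ between arms, so can the loss. Because the decision is left to each investigator, practice may also differ between sites. Protocol 9.2 bases sample size re-assessment on the primary endpoint and the 7-day DSRS, so the interim decision uses the same data.

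**Working it through.** **Timing.** Treatment is given on three consecutive days. Counting the first session as day 1, the last is day 3, the VFSS falls nominally on day 3 + 2 = 5, and the 7-day visit on day 3 + 7 = 10. Withdrawal before about day 5 loses the primary outcome; withdrawal before about day 10 loses FOIS and DSRS.

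**What each provision does for a patient withdrawn by the investigator for pneumonia treatment**

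| Provision | Effect |
|---|---|
| Protocol 7.1, encouragement to stay | Addresses the patient; does not limit the investigator's power in 7.2 |
| Protocol 7.2 and 9.3, kept in analysis and ITT | Keeps the patient in the set; supplies no outcome |
| Protocol 9.4.2 and SAP 4.6.1, multiple imputation | General intention to impute PAS; the method is tied to loss to follow-up or death and uses baseline data only, so it cannot reflect the pneumonia |
| Tipping-point analysis | Tests the primary result; does not reach FOIS or DSRS |
| SAP 4.6.2 | Secondaries tested without imputation |

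**The plan's own figures.** 180 / (1 − 0.20) = 225 and 270 / (1 − 0.20) = 337.5, rounded up to 338. Both reproduce. The initial dropout allowance is 225 − 180 = 45 patients.

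**Illustration for DSRS.** From SAP 4.2: planned difference 1.75, SD 4. Assumed, because the documents do not give them:
- 1:1 allocation, so 112.5 of 225 per arm
- pneumonia in 5–20% of sham and 3–12% of PES patients
- every case withdrawn before the 7-day visit
- withdrawn patients k = 2 to 4 DSRS points worse than retained patients in the same arm

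Patients lost = 112.5 × (p_sham + p_PES). Each arm's full mean equals its retained mean plus k × p, so the observed-case difference = 1.75 − k × (p_sham − p_PES).

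| p_sham / p_PES | Lost | Share of 45 | Fall (k = 2 to 4) | Observed difference |
|---|---|---|---|---|
| 5% / 3% | 112.5 × 0.08 = 9 | 20% | 0.04–0.08 | 1.71–1.67 |
| 10% / 6% | 112.5 × 0.16 = 18 | 40% | 0.08–0.16 | 1.67–1.59 |
| 20% / 12% | 112.5 × 0.32 = 36 | 80% | 0.16–0.32 | 1.59–1.43 |

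For scale, the standard error with 90 per arm is 4 × √(2/90) = 0.60. In this model the shift is zero if the two arms have equal rates and reverses sign if PES has more pneumonia.

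**Why background rates are not used directly.** Protocol 2.1 cites 16.4% and 44% in dysphagic cohorts. The first counts 11 cases in 67 admissions, two of them recurrences (9/67 = 13.4% on initial cases). The second is from tube-fed patients with severe dysphagia, mostly in the first 2–3 days. This trial enrols 7–28 days after stroke and excludes current pneumonia treatment.

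No matching figure is offered for the primary endpoint; the documents give no PAS distribution to build one on.

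**The case against.** Withdrawal is permitted, not required, and only where the criterion precludes participation; nothing says pneumonia does. The protocol otherwise treats pneumonia as an on-study event: it is assessed at 48 hours, day 7 and day 14 or discharge, listed as anticipated, and followed through antibiotic days. Discontinued patients stay in the analysis, missing PAS is to be imputed, and a tipping-point analysis is planned. The illustrated losses stay within the 45-patient allowance, the DSRS shift is at most about half a standard error (0.32/0.60), and in that scenario it works against PES. Deleting the one bullet would also achieve little, since the opening sentence and the adverse-event bullet reach the same patient.

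Most of this stands and limits the weight of the point. It does not remove it: none of these provisions says that such a patient must be followed, and none recovers the outcomes.

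A reader might go further in two ways that the documents do not support:
- That the pneumonia endpoint itself is biased. The pneumonia that triggers withdrawal would normally already be recorded as an endpoint event and an adverse event. The exposure is the data due afterwards.
- That such patients fall under no rule for the primary endpoint. The general statement that missing PAS is imputed covers them; what is unspecified is the method for this reason.

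**Conclusion.** The point holds as a gap in retention and missing-data wording that should be closed. Protocol 7.2 allows follow-up to end for a reason related to outcome and sits poorly with Protocol 7.1. The safeguards are partial for the primary endpoint and weaker for the 7-day secondaries. The size and direction of any bias cannot be determined from the documents. The figures of 9–36 patients and 0.04–0.32 DSRS points depend wholly on the assumed rates, complete withdrawal of cases before the 7-day visit, and the assumed 2–4 point gap; partial use of the provision would lose fewer patients.

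**What to change.** 1. In Protocol 7.2, separate stopping study treatment from ending follow-up, for the whole list including its opening sentence and the adverse-event bullet. State that exclusion criteria govern entry, and that meeting one after randomisation, or being found to have met one at entry, is not by itself a reason to end outcome collection. Such patients continue the scheduled assessments that the investigator judges can be done safely, unless consent is withdrawn. Leave treatment-stopping decisions as written, and reconcile 5.2, 7.1 and 7.2.
2. In Protocol 9.4.2 and SAP 4.6.1, apply the multiple imputation to patients with no post-treatment PAS for any reason, naming investigator withdrawal and withdrawal of consent.

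The first change matters more: the imputation uses baseline data only, and the secondaries are protected only by keeping patients in follow-up. The cost is wording in three sections and some follow-up of patients who would otherwise have been withdrawn. No new visits or procedures are needed.

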7.3 SITE TERMINATION AND STUDY TERMINATION

The sponsor may suspend or prematurely terminate an individual investigative site or terminate the entire study for the following reasons:

- A decision is made to suspend or discontinue testing, evaluation, or development of the investigational product for any reason
- An individual site may be closed for the following reasons:
 - The investigator fails to enroll patients into the study at an acceptable rate,
 - The investigator fails to comply with pertinent regulations of appropriate regulatory authorities,
 - Site personnel demonstrate insufficient compliance to protocol requirements, and/or
 - Site personnel submit knowingly false information from the research facility to the sponsor, study monitor, or appropriate regulatory authority

CONFIDENTIAL Page 44 of 71

An investigator, IRB/EC, or FDA may suspend or prematurely terminate a site's participation in a clinical investigation. The IRB/EC and FDA may suspend an investigation if a suspicion of unacceptable risk to patients arises; the sponsor shall terminate the investigation if an unacceptable risk is confirmed.

If the study is terminated early, all specified follow-up data on patients enrolled prior to termination will be collected and reported.

8 STUDY ASSESSMENTS AND PROCEDURES

8.1 STUDY ASSESSMENTS

8.1.1 SCREENING AND BASELINE ASSESSMENTS

In addition to the assessments detailed below, a medical history and demographics data will be collected at the screening visit. The medical history can be obtained from the patient's medical record and the physical assessment is part of standard care. A modified physical exam will be conducted at the baseline visit to establish the patient's current condition, to facilitate the appropriate adjudication of adverse events that may occur during the study. Information obtained from these assessments will be recorded on the eCRF. Informed consent will also be obtained, per standards and guidelines at each site.

8.1.2 NASOPHARYNGEAL EXAMINATION

The patient's nasopharynx will be examined by means of a visual exam using a standard flashlight /penlight at baseline, Day 7 post catheter placement and upon removal of catheter. If there is evidence or symptoms of erosion or trauma, a fiberoptic exam should be done to rule out any adverse events.

8.1.3 VIDEOFLUOROSCOPIC STUDY (VFSS)

The VFSS is a swallow test during which swallowing function is analyzed radiographically. Institutional protocols vary widely with respect to the consistencies of the contrast materials and the volumes of each; hence, a standardized approach will be used for all protocol-specific assessments. Baseline VFSS must meet the threshold criteria of demonstrating a PAS of \geq 4, in three of the six boli (5 mL/1 tsp/bolus), during swallowing "thin liquid" barium media as assessed by the clinical staff administering the VFSS.

Standardized VFSS Approach

The standardized VFSS examination will be administered using standardized, commercial preparations of barium sulfate media and will be comprised of two distinct phases:

- 1) Thin liquid: 5 mL/1 tsp/bolus x 6 swallows
- 2) Nectar liquid: 5 mL/1 tsp/bolus x 6 swallows

CONFIDENTIAL Page 45 of 71

Varibar® (Bracco Diagnostics, Inc. Monroe Township, NJ) will be used as the barium sulfate (40% w/V) media across all sites whenever possible to ensure standardization of the VFSS and its interpretation. Varibar is provided in pre-mixed, ready-to-use consistencies, and thus removes the uncertainty that comes with measuring and mixing prior to use. Varibar will be administered by the SLP/SLT personnel at each site per site standard practice. If Varibar is not used at a site, the site may use their standard as long as the consistency and viscosity is similar to that of Varibar.

Refer to section 7.1 for VFSS stopping criteria.

8.1.3.1 Penetration Aspiration Scale (PAS)

The PAS provides a scoring mechanism for airway closure and clearance during the VFSS. The PAS is a validated 8-point ordinal scale that quantifies penetration and aspiration events observed during VFSS²⁸. Scores are determined primarily by the depth to which material passes into the airway and the swallower's response to the material passing into the airway. For each swallow task, there may be more than one swallow. Each swallow in a task shall be scored via the PAS by the core lab.

Penetration Aspiration Scale

Score	Description			
1	Material does not enter airway			
2	Material enters the airway, remains above the vocal folds, and is ejected from airway			
3	Material remains above the vocal folds, and is not ejected from airway			
4	Material contacts the vocal folds, and is ejected from airway			
5	Material contacts the vocal folds, and is not ejected from airway			
6	Material passes below the vocal folds [glottis], and is ejected into larynx or out of airway			
7	Material passes below the vocal folds [glottis], and is not ejected from trachea despite effort			
8	Material enters the airway [passes glottis], and no effort is made to eject it			

8.1.4 BARTHEL INDEX

The Barthel Index is a widely-used measure of functional disability and a measurement of quality of life, as it measures the extent to which someone can function independently and has mobility in their activities of daily living (ADL) i.e., feeding, bathing, grooming, dressing, bowel control, bladder control, toileting, chair transfer, ambulation and stair climbing. It was developed for use in rehabilitation patients with stroke and other neuromuscular or musculoskeletal disorders. The BI is completed by the patient on the

CONFIDENTIAL Page 46 of 71

provided worksheet and the data are entered on the eCRF. It is completed at the baseline, 14-day, and 11-week visits. Details regarding the administration of the BI can be found in the eTMF.

